10.3 Analysis of Laboratory Data

Not applicable.

10.4 Analysis of Vital Signs

Vital sign measurements of systolic and diastolic blood pressure and heart rate will be summarized.

Each vital sign variable will be summarized for all visits (starting with Baseline) with the number of non-missing observations, mean and standard deviation, median, minimum and maximum. Mean change from baseline to each applicable post-baseline visit will be summarized for each vital sign variable, with the number of observations, baseline mean, and visit mean.

10.5 Other Safety Analyses

10.5.1 Best Corrected Visual Acuity (BCVA)

BCVA will be performed for both eyes at each follow-up visit.

BCVA for the study eye and fellow eye will be summarized by a categorical tabulation of the number of line change from baseline at each follow-up visit for the following categories:

- 3 lines or better than baseline (“Much Better”)
- 2 lines better than baseline (“Better”)

- Between 1 line worse and 1 line better than baseline (“No change”)
- 2 lines worse than baseline (“Worse”)
- 3 lines or worse than baseline (“Much Worse”)

10.5.2 Intraocular Pressure (IOP)

Intraocular pressure (IOP) is measured at each follow-up visit prior to pupil dilation for both eyes.

IOP of the study eye and fellow eye will be summarized for the raw IOP values and change from baseline at each visit with descriptive statistics by treatment group.

The IOP of the study eye will be summarized by three cut-off values at each follow-up visit:

- ≥ 35 mmHg,
- ≥ 30 mmHg, and
- ≥ 25 mmHg

In addition, the change from baseline IOP in the study eye of ≥ 10 mmHg increase will be analyzed.

10.5.3 Biomicroscopy

The biomicroscopy examinations are performed for both eyes at every follow-up visit. The following assessments are performed:

- Findings from conjunctiva (edema, hyperemia and subconjunctival hemorrhage), cornea (edema and superficial punctuate keratopathy), and iris/pupil (rubeosis iridis) using a 5-point scale (0=none, 0.5=trace, 1=mild, 2=moderate, 3=severe)

- Anterior chamber (flare) using a 5-point scale (0 = None, 1 = Faint, 2 = Moderate, 3 = Marked, 4 = Intense).
- Cells of anterior chamber using a 6-point scale (0 = 0 cells, 0.5 = 1-5 cells, 1 = 6-15 cells, 2 = 16-25 cells, 3 = 26-50 cells, 4 = >50 cells)
- Iris/Pupil using a 5-scale in cells (0=no visible rubeosis iridis, +0.5= trace visible rubeosis iridis, +1=obvious vessels in 1 quadrant, +2= obvious vessels in 2-3 quadrants, +3= obvious vessels in 4 quadrants).
- Hypopyon of anterior chamber (not evaluable, present or not and the level estimated in millimeters)
- Lens status as phakic, pseudophakic, or aphakic
- Presence and severity of nuclear, cortical, and posterior subcapsular cataract lens opacities using a 3-point scale for each type of opacity (1 = opacity is absent, 2 = opacity is present, but less than standard photo #2, and 3 = opacity is present and as severe as or worse than standard photo #2)
- Posterior capsule assessment for aphakic or pseudophakic eyes as not evaluable, intact or not

The number and percent of patients with clinically significant biomicroscopy findings at one or more visits will be tabulated for study eye and fellow eye. A clinically significant finding is defined as at least two severity grade increase (worsening) from baseline, or a status change from absent to present or non-evaluable to evaluable at follow-up visits. If a

pathology is recorded at a follow-up visit but not at baseline, the baseline will be imputed with the same pathology, with a grade of zero (none).

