7.2 Lens Assessment

Lens Status:

Lens status will be assessed as phakic, pseudophakic, or aphakic. The lens (including the posterior capsule when visible, e.g., post-lens extraction) will also be evaluated for pathology. If pathology is present, it will be described.

Cataract Assessment (Phakic eyes only):

Under dilated examination, the presence and severity of nuclear, cortical, and posterior subcapsular cataract lens opacities will be evaluated according to the Age-Related Eye Disease Study Clinical Lens Grading Protocol. Biomicroscopic findings will be compared with standard photographs. AbbVie will supply the site with a copy of the standard photographs.³

Pupils should be dilated to at least 5 mm. The slit lamp should be used at 10x magnification. Grading will be performed as described below.

- Nuclear Sclerosis
 - Adjust the slit beam to a width of 0.3 mm and a height of 8.0 mm.
 - Orient the slit beam at 45° to the viewing axis.
 - Compare the slit lamp appearance with Nuclear Standard Photograph #2. The primary considerations are: the opalescence (reflectance) of the nucleus and the blurring of the normal landmarks, i.e., the dark interval at the center of the nucleus (the "sulcus") and the short, bright bands adjacent to it anteriorly and posteriorly (the "lentils," so named for their somewhat bean-like shape).
 - Standard Photographs. Only Nuclear Standard Photograph #2 is used in grading. Standard Photographs #1 and #3 are provided as examples of lenses that have less and more nuclear sclerosis than Standard Photograph #2.
 - Grading scale
 - I. Opacity is absent
 - II. Opacity is present, but less than Standard Photograph #2
 - III. Opacity is present and as severe as or worse than Standard Photograph #2
- Posterior Subcapsular (PSC) Opacities
 - Use retroillumination and include PSC opacities visible with it.
 - Standard Photographs. Only PSC Standard Photograph #2 is used for grading. PSC Standard Photograph #2 with lines at the borders of the opacity is provided for reference.
 - Grading scale
 - IV. Opacity is absent
 - V. Opacity is present, but less than Standard Photograph #2
 - VI. Opacity is present and as severe as or worse than Standard Photograph #2
- Cortical Opacities
 - Use retroillumination.
 - Include both anterior and posterior cortical opacities that are visible with retroillumination.
 - Combine all opacities and compare total area with Cortical Standard Photograph #2 (about 25% of the visible lens).

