10.5.4 Ophthalmoscopy

The ophthalmoscopy examinations are performed for both eyes at each follow-up visit. The following assessments are performed:

- Vitreous cells and vitreous haze using a 6-point rating scale plus not evaluable (0, 0.5, 1, 2, 3, 4 and not evaluable)
- Vitreous hemorrhage using a 6-point rating scale (0, 0.5, 1, 2, 3, and 4)
- Posterior vitreous detachment evaluated as no, yes and not evaluable
- Disc hemorrhage and other disc pathology as not evaluable, no finding or present
- Fundus as no finding or present
- Intraretinal fluid, subretinal fluid, intraretinal hemorrhage, rhegmatogenous detachment, tractional detachment, pigment epithelial detachment as no finding or present
- Retinal hemorrhage, retinal tear, rhegmatogenous retinal detachment, tractional retinal detachment, exudative retinal, other retinal detachment, round (astrophic) retinal holes, and lattice degeneration as no finding or present
- Cup to disc ratio value

Similar to biomicroscopy data, the number and percent of patients with clinically significant ophthalmoscopy findings at one or more visits will be tabulated for study eye and fellow eye. A clinically significant finding is defined as at least two severity grade increase (worsening) from baseline, or a status change from absent to present or non-evaluable to evaluable at follow-up visits.

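### On the 3-level lens scale, the two-grade rule can never flag progression of an opacity already present

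*SAP*

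**What the plan says.** SAP 10.5.3 (Biomicroscopy) tabulates, for study eye and fellow eye, the patients flagged at any follow-up visit. The flag is: "A clinically significant finding is defined as at least two severity grade increase (worsening) from baseline, or a status change from absent to present". The sentence goes on to add a move from non-evaluable to evaluable. SAP 10.5.4 (Ophthalmoscopy) repeats both parts of the rule; its status clause reads "or a status change from absent to present or non-evaluable to evaluable at follow-up visits". These counts are the only summaries of the graded examination data that the two sections specify.

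One rule therefore serves scales of different shapes:

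- **Lens opacity** (nuclear, cortical, posterior subcapsular): "using a 3-point scale for each type of opacity", where 1 is absent and 2 and 3 are both present. The Operations Manual (Protocol Appendix F), section 7.2, has the same three levels for phakic eyes; its middle level for nuclear sclerosis is "II. Opacity is present, but less than Standard Photograph #2".
- **Conjunctiva and cornea:** "using a 5-point scale (0=none, 0.5=trace, 1=mild, 2=moderate, 3=severe". Rubeosis uses the same five values.
- **Anterior chamber cells:** "Cells of anterior chamber using a 6-point scale (0 = 0 cells, 0.5 = 1-5 cells, 1 = 6-15 cells", continuing up to 4.
- **Vitreous:** "Vitreous cells and vitreous haze using a 6-point rating scale plus not evaluable (0, 0.5, 1, 2, 3, 4 and not evaluable". Vitreous hemorrhage uses the same six values.
- **Flare:** 0, 1, 2, 3, 4, with no half-step.

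SAP 10.5.3 also sets the baseline to grade zero when a pathology is recorded at follow-up but was not recorded at baseline. SAP 10.5.4 has no such sentence.

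**The concern.** A two-grade threshold needs a scale with room for two grades. Once an opacity is present, the lens scale has only one grade left, so the rule appears unable to register progression.

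The lens is a relevant structure in this study. Protocol 2.1 says the updated applicator changes the needle-sleeve feature that governs depth of penetration. SAP 10.2.6 itself lists lens changes among the events possibly related to implant position and administration. The examination table is the one place where graded lens data on every phakic eye could be compared between applicators without depending on an adverse event being reported.

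Two lesser points come from the same sentence. The status clause is not expressly limited to yes/no items, and a grade is not defined on scales that include 0.5.

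**Working it through.** The plan states no figure to reproduce. The check lists every possible worsening on each scale (with k levels there are k(k − 1)/2) and applies the rule under each reading. *Steps* counts positions on the scale; *units* counts numeric difference. The status clause is read either as covering all items or as covering ungraded items only.

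**1. Lens scale 1, 2, 3.** Possible worsenings: 3 × 2/2 = 3. There is no half-step, so steps and units agree.

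| Worsening | Grade change | Absent to present? | Status clause covers all items | Status clause covers ungraded items only |
|---|---|---|---|---|
| 1 to 2 | 1 | yes | flagged | not flagged |
| 1 to 3 | 2 | yes | flagged | flagged |
| 2 to 3 | 1 | no | **not flagged** | **not flagged** |

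The rule flags 2 of 3 worsenings under the wide reading and 1 of 3 under the narrow one. From grade 2 it flags 0 of 1 under both.

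**2. Imputed baseline on the lens scale.** Take an eye at grade 2 at follow-up.

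- Baseline recorded as absent: 2 − 1 = 1, which does not meet the two-grade limb.
- Baseline unrecorded and imputed as zero: 2 − 0 = 2, which meets it in units.

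The same assumed starting state (no opacity) gives two answers because zero lies off the scale. Imputing 1 removes the discrepancy.

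**3. Scales with a 0.5 level.**

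| Scale | Worsenings | Two steps | Two units | Steps plus status clause | Units plus status clause |
|---|---|---|---|---|---|
| 0, 0.5, 1, 2, 3 | 5 × 4/2 = 10 | 6 | 4 | 7 | 6 |
| 0, 0.5, 1, 2, 3, 4 | 6 × 5/2 = 15 | 10 | 8 | 11 | 10 |

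Steps and units disagree on two changes: 0 to 1 (two steps, 1 unit) and 0.5 to 2 (two steps, 1.5 units). If the status clause covers graded items, 0 to 1 is flagged anyway and only 0.5 to 2 stays ambiguous. Under that wide reading 0 to 0.5 is flagged. Under the narrow reading it is one step or 0.5 unit, and is not.

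**4. Flare 0 to 4.** Of 10 worsenings, 6 meet the two-grade limb by steps or units, and 7 are flagged if the status clause is added. The extra one is 0 to 1.

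**The case against.** The strongest reply is that lens progression is captured elsewhere. Protocol 6.1 treats worsening of a pre-existing condition as an adverse event. SAP 10.2.6 and Appendix B tabulate cataract and lens changes reported as adverse events, and SAP 10.5.1 tabulates change in visual acuity. This stands: a reader might infer that damage to an already cloudy lens would go unseen in this trial, and the documents do not support that. But the adverse-event route needs the investigator to report an event, in an open-label study. It does not make the examination rule work on its own scale.

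The gap is also per opacity type. Under the wide reading, a new type (1 to 2) in an eye that already has another type is flagged. This stands too.

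On the half-step scales, a reader might infer that the rule wrongly flags every trace change and that such findings would fill the table in both arms. That goes too far. The sentence contrasts a severity grade with a status, and both sections list graded items separately from present/absent ones, so the status clause can fairly be read as confined to the latter. The documents give no rates of trace findings and show no bias between arms. Counting any new finding after an injection is also a defensible cautious screen. Nor do the two secondary points add together at full size: if the status clause reaches graded items, the step/unit gap on the 5-point scale shrinks from 6 against 4 to 7 against 6.

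Finally, the study has no hypothesis and follows subjects for 7 days, so a change from 2 to 3 may be rare.

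**Conclusion.** The lens point holds under every reading. Progression of an opacity type from 2 to 3 cannot be flagged in the biomicroscopy table, and the imputed zero is not a lens grade. This is a stated rule that does not fit its scale, not merely a missing definition.

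Its size can be given only as transitions: 1 of 3 possible worsenings, and the only one available to an existing opacity. The documents do not say how many phakic eyes will enter at grade 2, so no number of missed subjects can be given. Eyes at grade 3 at baseline have no room to worsen on this scale under any rule.

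The trace and step/unit points are requests for clarification. They matter because two programmers could produce different tables from the same data; they do not show that the rule gives wrong results. All these tables are descriptive, so no alpha, power or sample size changes.

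**What to change.** **Main change, SAP 10.5.3.** For each lens opacity type (nuclear, cortical, posterior subcapsular), count any increase of one grade or more from baseline as a finding, and impute an unrecorded baseline as grade 1 (absent). All 3 possible worsenings are then flagged, and 1 to 2 stays flagged however the status clause is settled. Make the two changes together: under a one-grade rule, a program that imputed zero could read a follow-up grade of 1 (absent) as an increase, since 1 − 0 = 1.

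**Clarification, SAP 10.5.3 and 10.5.4.** State which items the status clause covers and define a grade. One option is to confine the status clause to ungraded items and define two grades as two ordinal steps. New mild findings (0 to 1) on the half-step scales then stay flagged, and 0 to trace does not.

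**Cost.** SAP wording before database lock, using data already planned. Some one-grade grader variation on the lens will be flagged. An opacity that was present but ungraded at baseline would count as new, as it can under the present convention. With the option above, new faint flare (0 to 1) would not be flagged, because that scale has no half-step; if it should be, say so. Confining the status clause and choosing two units instead would cost more: new mild vitreous hemorrhage or anterior chamber cells (0 to 1) would drop out.

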10.5.4 Ophthalmoscopy

The ophthalmoscopy examinations are performed for both eyes at each follow-up visit. The following assessments are performed:

- Vitreous cells and vitreous haze using a 6-point rating scale plus not evaluable (0, 0.5, 1, 2, 3, 4 and not evaluable)
- Vitreous hemorrhage using a 6-point rating scale (0, 0.5, 1, 2, 3, and 4)
- Posterior vitreous detachment evaluated as no, yes and not evaluable
- Disc hemorrhage and other disc pathology as not evaluable, no finding or present
- Fundus as no finding or present
- Intraretinal fluid, subretinal fluid, intraretinal hemorrhage, rhegmatogenous detachment, tractional detachment, pigment epithelial detachment as no finding or present
- Retinal hemorrhage, retinal tear, rhegmatogenous retinal detachment, tractional retinal detachment, exudative retinal, other retinal detachment, round (astrophic) retinal holes, and lattice degeneration as no finding or present
- Cup to disc ratio value

Similar to biomicroscopy data, the number and percent of patients with clinically significant ophthalmoscopy findings at one or more visits will be tabulated for study eye and fellow eye. A clinically significant finding is defined as at least two severity grade increase (worsening) from baseline, or a status change from absent to present or non-evaluable to evaluable at follow-up visits.

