7 APPENDICES

7.1 Biomicroscopy Exam (slit lamp)

Biomicroscopic examinations will be performed using a slit lamp. The examinations will include determination of ophthalmic medical observations/complications, evaluation of the condition of the eyelids, conjunctiva, cornea, anterior chamber, iris/pupil, and lens.

Eyelid/Eyelid Margins/Lashes:

Edema

0 (None) = No edema
+0.5 (Trace) = Localized, minimal (trace) swelling
+1 (Mild) = Localized, mild swelling
+2 (Moderate) = Diffuse, moderate swelling
+3 (Severe) = Diffuse, severe swelling

Erythema

0 (None) = No erythema
+0.5 (Trace) = Localized, minimal (trace), flush reddish color
+1 (Mild) = Localized, mild, flush reddish color
+2 (Moderate) = Diffuse reddish color encompassing the entire lid margin
+3 (Severe) = Deep diffuse reddish color of lid margins and superior and/or inferior eyelid

Conjunctiva (Bulbar):

Hyperemia

0 (None) = No hyperemia
+0.5 (Trace) = Minimal (trace) flush, reddish color
+1 (Mild) = Mild flush, reddish color
+2 (Moderate) = Bright red color
+3 (Severe) = Deep, bright, diffuse redness

Edema

0 (None) = No edema
+0.5 (Trace) = Localized, minimal (trace) swelling
+1 (Mild) = Localized, mild swelling
+2 (Moderate) = Diffuse, moderate swelling
+3 (Severe) = Diffuse, severe swelling

Conjunctiva (Palpebral):Hyperemia

0 (None) = No hyperemia
+0.5 (Trace) = Minimal (trace) flush, reddish color
+1 (Mild) = Mild flush, reddish color
+2 (Moderate) = Bright red color
+3 (Severe) = Deep, bright, diffuse redness

Edema

0 (None) = No edema
+0.5 (Trace) = Localized, minimal (trace) swelling
+1 (Mild) = Localized, mild swelling
+2 (Moderate) = Diffuse, moderate swelling
+3 (Severe) = Diffuse, severe swelling

Cornea:Edema

0 (None) = No edema
+0.5 (Trace) = Localized, minimal (trace) epithelial haze
+1 (Mild) = Dull glass appearance of epithelium that may include fine localized microcystic changes
+2 (Moderate) = Dull glass appearance of the epithelium with large number of cystic changes with or without stromal edema
+3 (Severe) = Epithelial bullae and/or stromal edema, localized or diffuse, with or without stromal striae

Punctate Epithelial Staining (includes superficial punctate keratopathy, punctate epithelial erosion, and punctate epithelial keratopathy)

0 = No staining
+0.5 = Trace
+1 = Mild
+2 = Moderate
+3 = Severe

Anterior Chamber:

For the measurements of cells and flare based on Standardized Uveitis Nomenclature (SUN) criteria², the following settings should be used:

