- 1 x 1 mm slit beam
- High magnification
- Highest slit lamp voltage
- Low ambient lighting

- Illumination angle of 45°
- Same grader and slit lamp whenever possible

The Anterior Chamber will be evaluated, at a minimum, for presence of the following pathologies:

- Cells
 - 0 = 0 cells
 - +0.5 = 1-5 cells (trace)
 - +1 = 6-15 cells
 - +2 = 16-25 cells
 - +3 = 26-50 cells
 - +4 = > 50 cells
- Flare
 - 0 = None: No flare seen
 - +1 = Faint: Faint flare seen
 - +2 = Moderate: Iris and lens details clear
 - +3 = Marked: Iris and lens details hazy
 - +4 = Intense: Fibrin or plastic aqueous
- Anterior Synechiae
- Hypopyon – if hypopyon is present provide details and if applicable levels in millimeters (mm)

Iris/Pupil:

The iris/pupil will be evaluated for pathology. If pathology is present, it will be described.

Rubeosis Iridis

- 0 = No visible rubeosis iridis
- +0.5 = Trace visible rubeosis iridis
- +1 = Obvious vessels in 1 quadrant (≤ 90 degrees)
- +2 = Obvious vessels 2-3 quadrants (91-270 degrees)
- +3 = Obvious vessels 4 quadrants (271-360 degrees)

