7.3 Ophthalmoscopy (indirect)

Dilated Fundoscopic Examination

The fundus assessments should be conducted through a dilated pupil. The examinations will include evaluation of the lens, vitreous, optic nerve, macula, and retina. The investigator should note if the pupil dilated normally.

Vitreous:

(1 x 3 mm beam in anterior vitreous).⁴

Cells

0 = None
+0.5 = 1-10 cells
+1 = 11-20 cells
+2 = 21-30 cells
+3 = 31-100 cells
+4 = > 100 cells

Note if the condition is not evaluable.

Vitreous Haze

Vitreous haze will be graded by viewing the optic disc and posterior retina using the following settings and by comparing the haze against a photographic standardized scale⁵ according to the chart provided by AbbVie.

- Indirect ophthalmoscope and a 20-diopter lens
- Illumination set to mid-power
- Large beam
- Low ambient lighting
- Same grader and indirect ophthalmoscope whenever possible

The scale is categorized as follows:

0 = No inflammation

+0.5 = Trace inflammation (slight blurring of the optic disc margins and/or loss of the nerve fiber layer reflex)

+1 = Mild blurring of retinal vessels and optic nerve

+2 = Moderate blurring of optic nerve head

+3 = Marked blurring of optic nerve head

+4 = Optic nerve head not visible

Note if the condition is not evaluable.

Vitreous Hemorrhage

Vitreous hemorrhage will be evaluated for severity. Indicate whether or not it is localized to the injection site.

0 = No visible evidence of hemorrhage on fundus ophthalmoscopic exam

+0.5 = Retinal detail is visible; trace hemorrhage is present

+1 = Retinal detail is visible; mild hemorrhage is present

+2 = Large retinal vessels are visible; central retinal detail is not visible

+3 = Red reflex is visible; no central retinal detail is seen posterior to the equator

+4 = No red reflex

Posterior Vitreous Detachment

The presence or absence of a posterior vitreous detachment will be evaluated. Note if the condition is not evaluable.

Optic Nerve:

The optic nerve will be evaluated for pathology. If pathology is present, it will be described. It will be noted if the condition is not evaluable.

Cup/Disc ratio will be reported using a 0.0 to 1.0 scale. It will be noted if the condition is not evaluable.

Macula:

The macula will be evaluated, at a minimum, for the presence or absence of the following pathologies. Note if the condition is not evaluable.

- Intraretinal fluid
- Subretinal fluid
- Intraretinal hemorrhage
- Subretinal hemorrhage
- Rhegmatogenous detachment

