- Tractional detachment
- Pigment epithelial detachment

Retina Periphery:

The retina periphery will be evaluated, at a minimum, for presence or absence of the following pathologies. Note if the condition is not evaluable.

- Retinal hemorrhage
- Retinal tear (specify location in clock hours)
- Rhegmatogenous retinal detachment with or without macular detachment
- Tractional retinal detachment with or without macular detachment
- Exudative retinal detachment with or without macular detachment
- Round (atrophic) retinal hole
- Lattice degeneration

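### The eye-finding lists in SAP 10.5.3 and 10.5.4 do not match what Operations Manual 7.1 and 7.3 collect, and an unseen macula or peripheral retina has no stated handling

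*SAP*

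**What the plan says.** **Posterior segment.** For the macula, Operations Manual 7.3 instructs: "The macula will be evaluated, at a minimum, for the presence or absence of the following pathologies. Note if the condition is not evaluable". Its list of seven findings includes "Subretinal hemorrhage". For the periphery it gives the same instruction: "The retina periphery will be evaluated, at a minimum, for presence or absence of the following pathologies. Note if the condition is not evaluable". SAP 10.5.4 lists the macular items as "Intraretinal fluid, subretinal fluid, intraretinal hemorrhage, rhegmatogenous detachment, tractional detachment, pigment epithelial detachment as no finding or present", and its peripheral list ends "round (astrophic) retinal holes, and lattice degeneration as no finding or present".

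**Anterior segment.** Operations Manual 7.1 requires "evaluation of the condition of the eyelids, conjunctiva, cornea, anterior chamber, iris/pupil, and lens". It gives graded scales for eyelid edema and eyelid erythema and, under the anterior chamber, lists "Anterior Synechiae". SAP 10.5.3 opens its graded items with "Findings from conjunctiva (edema, hyperemia and subconjunctival hemorrhage", scored from none to severe. It has no eyelid item and no synechiae item.

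**Tabulation rule.** Both SAP sections count patients who have a clinically significant finding at any follow-up visit. Significant means a worsening of two or more severity grades from baseline, a change from absent to present, or a change from non-evaluable to evaluable.

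**The concern.** The SAP lists are the only statement of which examination items feed the significant-findings tables. If they differ from what sites record, collected data have no assigned place in the report, and the programmer has to choose how to treat a retina that could not be seen.

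This matters somewhat more here than in most descriptive safety sections. The applicator changes include the needle sleeve, which is the depth-of-penetration feature (protocol 2.1). Operations Manual 3.12 names vitreous hemorrhage, retinal tear and retinal detachment as procedure-related complications to look for after injection. A retina that cannot be seen is also foreseeable: the upper grades of the manual's own vitreous hemorrhage scale are defined by loss of retinal detail or of the red reflex. Treatment is open-label, so the handling is better fixed in writing before the tables are produced.

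**Working it through.** The point depends on no power, rate or error calculation. The check is an item-by-item comparison, followed by applying the SAP rule to example patients.

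1. **Macula.** The manual has 7 items and the SAP has 6, in the same order: 7 − 6 = 1 missing, subretinal hemorrhage. The SAP adds none.
2. **Peripheral retina.** All 7 manual items are in the SAP, which adds other retinal detachment: 7 + 1 = 8. Nothing is missing from the list itself.
3. **Evaluability.** The manual asks sites to note it for both macula and periphery. The SAP allows two levels only, no finding or present. This is not a general convention of the section: SAP 10.5.4 keeps a not-evaluable level for vitreous cells, vitreous haze, posterior vitreous detachment and disc findings. Its significance rule therefore uses a status that the macula and periphery items cannot take.
4. **Biomicroscopy and lens.** Count bulbar and palpebral conjunctiva together and the three cataract types as one. Operations Manual 7.1 and 7.2 then give 14 items. The SAP omits 3 (eyelid edema, eyelid erythema, anterior synechiae) and adds 1 (subconjunctival hemorrhage): 14 − 3 + 1 = 12 items in SAP 10.5.3.
5. **Scale.** The manual's conjunctiva sections define grades for hyperemia and edema only. The SAP's two-grade rule for subconjunctival hemorrhage therefore rests on grades that the manual does not define.

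The SAP rule applied literally to example patients:

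- *Eyelid erythema rises from 0 to +2, nothing else changes.* The change meets the two-grade rule, but the item is not listed, so the patient is not counted.
- *Anterior synechiae or subretinal hemorrhage goes from absent to present, nothing else changes.* The change meets the absent-to-present rule, but the item is not listed and has no row.
- *Periphery cannot be seen at Day 2 and is clear at Day 7.* The Day 2 value could be set to no finding, set to missing, or excluded; the SAP does not say which. If the periphery is seen at neither visit, the SAP does not say whether the eye stays in the denominator. The non-missing denominator in SAP 7.0 is stated for demographics, baseline characteristics, history and medications, not for these tables.
- *Macula not evaluable at baseline, visible and normal at Day 2.* If the missing level were added and the rule left as it is, this eye would be flagged as significant only because it became visible. An eye going from visible to unseen would not be flagged on those items.

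The last example shows that the level and the rule have to be changed together.

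**The case against.** The strongest reply is that the lists describe the examinations performed and do not limit what is tabulated. The counting sentence covers significant findings in general. SAP 10.5.3 gives a baseline grade of zero to any pathology first recorded at follow-up, without restricting this to listed items. SAP 10.5.4 also has a broad fundus item, and the adverse event terms in SAP 10.2.6 and Appendix B include retinal hemorrhage and other retinal abnormality. This stands in part: a subretinal hemorrhage need not vanish from the report. But the SAP does not define what the fundus item covers, an adverse event term is not an examination finding, and neither route gives the finding its own row. Neither the fundus item nor those two retinal terms reach eyelid findings or synechiae.

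Three stronger readings are tempting, and the documents do not support them.

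- *Unseen eyes are counted as clear, so tears and detachments are understated.* No SAP text codes an unseen retina as no finding; it could equally be left missing. A new vitreous hemorrhage that rises from 0 to +2 or more meets the two-grade rule on its own scale, so that eye is flagged anyway. Vitreous hemorrhage is also on the adverse event list.
- *The effect can be sized as a share of the test eyes.* That needs an assumed number of unseen eyes, which the documents do not give. A count at a single visit does not fit a table built over all follow-up visits, because an eye obscured at Day 2 and seen at Day 7 still contributes.
- *Sites have no definitions for grading subconjunctival hemorrhage.* The eCRF is not in the documents and may hold a scale; SAP 7.3 and 10.2.1 define other variables by eCRF fields. The manual also grades punctate epithelial staining by severity labels alone, so labels without descriptors are not unusual here.

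**Conclusion.** The mismatch is real and minor. Four items that the manual requires are absent from the SAP lists: subretinal hemorrhage, eyelid edema, eyelid erythema and anterior synechiae. The macula and periphery items lack a not-evaluable level that the manual requires and that the SAP's own rule presupposes. One item is graded without a scale in the manual.

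Read literally, a patient whose only new finding is one of the four would not be counted in the significant-findings tables as having that finding, and the counting of an unseen macula or periphery is left open. The first part assumes that the lists define what is tabulated and that the undefined fundus item is not taken to include subretinal hemorrhage. The consequence is confined to descriptive safety tables. No percentage can be attached to it from the documents, and sample size, type I error and the applicator assessment are unaffected.

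**What to change.** In the SAP:

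- Add subretinal hemorrhage to the macula list in 10.5.4, and eyelid edema, eyelid erythema and anterior synechiae to 10.5.3.
- Add a not-evaluable level to the macula and periphery items, show its count, and use as the denominator the eyes evaluable at one or more follow-up visits.
- In the same revision, change the criterion that counts a move from non-evaluable to evaluable, so that an eye is not flagged merely because its retina became visible. State how a finding first seen after a non-evaluable baseline is counted. The criterion stands in both 10.5.3 and 10.5.4.
- For subconjunctival hemorrhage, cite the scale used on the eCRF, or report it as present or absent.

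The cost is SAP wording and the matching table shells. Every item added is already required by the Operations Manual, so no visit, procedure or new data collection is needed.
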